SPMS participants using intention-totreat analysis. [name] et al conducted a single-center, 2-year randomized, double-blind, placebo-controlled phase 2 trial (n=51) of daily oral LA in SPMS (18). The LA cohort demonstrated a 68% reduction in the annualized rate of whole brain atrophy (0.21% vs -0.65%, p = 0.002, Fig 4). Although not powered to detect clinical outcomes, the LA cohort had a trend toward improvement in walking speed in the T25FW (-0.54 SD 0.36 vs 0.14 SD 0.25, p = 0.06). Overall LA was safe and well tolerated with high compliance and at the time, no unexpected deleterious adverse events (AE) were attributed to LA. A later review of AE's in light of safety data emerging from the present study indicate that the serious

adverse event of biopsy-proven glomerulonephritis and a second case of proteinuria in subjects in the LA cohort was related to lipoic acid (see above). To date, all three cases resolved within a 3-12 month period. Gastrointestinal (GI) upset was significantly greater in the LA cohort compared to placebo (17% v 3% p = 0.004). Unexpectedly, the LA cohort had a significantly lower number of falls than the placebo cohort (15% v 38%, p = 0.03). The results of this study formed the basis of the current research trial.

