a. Proteinuria monitoring: Subjects must have urine protein *monitored every 3 months* for the duration of the study. Subjects must pause study drug if they skip or miss a visit until draw can occur.

Subjects with baseline (screening) negative or trace proteinuria may participate in the study. Subjects with baseline 1+ or higher proteinuria are further tested for albumin to creatinine ratio (ACR): 1) ACR \leq 300mg/g may participate, 2) ACR >300mg/g are excluded and receive referral to PCP. No repeat screening for proteinuria in subjects who have ACR >300mg/g will be done.

Subjects who experience 1+ or higher proteinuria during the study are further tested for ACR: 1) ACR \leq 300mg/g may continue participation, 2) ACR >300mg/g permanently stop study drug and receive referral to PCP or nephrologist along with notification of the Medical Monitor. A referral to Nephrology is recommended if ACR>1000mg/g. A kidney biopsy is recommended if proteinuria >300 does not resolve within 6 weeks of drug cessation.

b. Renal function monitoring: Subjects with baseline eGFR ≥ 60 may participate in the study. Subjects with baseline eGFR<50 are excluded. Subjects with baseline eGFR 50-59.9 are retested: 1) eGFR ≥ 60 may participate in the study, 2) eGFR<60 are excluded.

Subjects who experience eGFR 50-59.9 during the study are retested within 1 month: 1) eGFR \geq 60 may continue participation in the study, 2) eGFR<60 permanently stop study drug and are referred to PCP. Subjects who experience eGFR<50 during the study permanently stop study drug and referred to PCP. Regardless of the eGFR, if the eGFR decreases by 25% or more compared to the baseline eGFR, the Medical Monitor should be notified and should review the information to determine the next course of action.

c. Liver function monitoring: Abnormal liver laboratory results are graded according to the Common Terminology Criteria for Adverse Events v5.0 (https://ctep.cancer.gov/protocoldevelopment/electronic_applications/ctc.htm).

Subjects who have stable and asymptomatic baseline Grade 1 abnormal laboratory liver values may, at the discretion of the site treating neurologists, participate in the study. Subjects who experience laboratory abnormalities of Grade 1 during the study will be permitted to continue at the full dose of study drug unless advised otherwise by the DSMB or other monitoring entities.

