Abnormal laboratory tests may be repeated immediately if laboratory testing error is suspected. Laboratory tests should be repeated within 1 month for any liver values reaching a Grade 2 or greater.

If laboratory liver value(s) are still Grade 2 or greater by 1 month, the investigational drug will be reduced by 50% and levels checked again within 1 month. The rationale is that liver-related abnormalities are often dose-dependent. If laboratory liver value(s) improve to Grade 1 or less, the study drug dose is then increased to the full dose. If the same subsequent laboratory value(s) worsen again at the full dose, the subject may continue for the study duration at the 50% dose as long as subsequent laboratory values do not meet Grade 2 or greater levels. If subjects on a 50% dose demonstrate continued Grade 2 value(s) at a maximum of 1 month, subjects should stop the investigational drug. Those subjects for whom laboratory values do not improve to Grade 1 or better levels after 2 months off study drug permanently stop study drug. Only two investigational drug cessations are allowed for each subject. Any subject who experiences a third Grade 2 or higher laboratory test must permanently discontinue the investigational drug. If in question, permanent study drug discontinuations can be discussed with the Medical Monitor to establish the relationship of the laboratory result to the investigational drug. Subjects continue study procedures following the study flowsheet until study end during any investigational drug dose reductions and temporary cessations (see 5.1d for special handling of MS clinical relapse evaluations).

Safety laboratory results will be reviewed by site treating neurologists within 3 business days to determine if dose adjustments or safety reporting is required along with documentation and reporting as required (section 6.0 Reporting).

Sexually active female subjects capable of becoming pregnant and female partners of sexually active male subjects will be asked to use effective birth control during the study. If a female participant or partner of a male participant becomes pregnant during the research study, study personnel must be notified immediately. Subjects will be advised not to breastfeed while taking this investigational drug. Screening for pregnancy in female subjects of child-bearing potential will be conducted via pregnancy tests at study visits.

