5.6 Data Analysis

5.6a. Sample size: The sample size and power analysis were based on the pilot LA in SPMS trial in which LA had improved time to complete the T25FW (-0.54 seconds SD 0.36 vs 0.14 SD 0.25, p = 0.06). A sample size of 44 per group will have 80% power to detect a difference between the LA group with a coefficient, β_1 regression slope of -0.50 seconds and the placebo group coefficient, β_2 slope of -1.00, assuming that the standard deviation of the difference between the groups is 2.20 and the standard deviation of the residuals (repeated measures within each participant) is 1.80 with a 0.05 two-sided significance level and the correlation of 0.85 between the measurements over time, which if lower increases the power. The delta of improvement is a reduction in the rate of walking slowing of 0.5 seconds per unit of time. This translates into 2 seconds on the average timed walk over 2 years. A sample size of 59 per arm will allow for a 25% drop-out rate. The pilot study had a 10% drop out rate however 25% is more realistic for a multi-site trial in an era with more therapeutic options for MS. Screen visit failures are likely to be minimal (<10% of all screen visits) as most eligibility requirements can be made prior to the screening visit using the methods described in 5.2 Recruitment Methods.

As a check on these calculations we compared the estimates, Altmann et al.'s estimates of sample size when using SIENA as the method of determining whole brain atrophy rate, the current sample of 44 per group will achieve 80% power at significance level 0.05 assuming a 40-50% effect size (33).

5.6b. Data analysis plan: Data is analyzed by the SCC at study completion or at any point requested by the DSMB. Only subjects that complete the baseline evaluation and take at least one dose of study drug will be included in the data analysis.

The SCC will use the mixed model approach to compare, between the treatment groups, mean rates of change from baseline in the times to complete the T25FW. The SCC will use the transformation 25/T25FW, which is the walking speed in feet per

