Adverse and serious adverse events will be tabulated and compare the differences in the occurrence and the frequencies between the two groups. The frequency of side effects will be compared using χ^2 tests or Fisher's exact test as appropriate depending on the number of adverse events seen. For evaluation of patient safety, laboratory test results at baseline and changes from baseline will be summarized and compared using t-tests for continuous measures and Fisher's exact test for proportions.

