5.7 Withdrawal of Subjects

Subjects can withdraw from the study at any time. Reason for withdrawal will be recorded. Subjects may also be withdrawn from the study by LSIs and in agreement with the study PI for any of the following reasons: 1. New or worsening medical conditions (e.g., cancer, renal disease, end-stage cardiopulmonary disease, post-traumatic stress disorder, uncontrolled diabetes, etc.) that may interfere with study procedures or otherwise pose concern for subject health or safety, 2. New pregnancy, 3. Inability of subjects to comply with study procedures, 4. Other reasons deemed important to subject safety or data quality raised by the DSMB, IRB, FDA, or any other regulatory body that has the authority to do so. If subjects are deemed no longer safe to take the investigational drug but otherwise are able to participate in the study outcomes for the remainder of the study, they are encouraged to do so.

Female study subjects of childbearing potential will be encouraged to use effective birth control methods during the study. Pregnancy testing in female subjects of childbearing potential will be conducted as part of safety laboratory studies at each study visit according to the study flowsheet. Should pregnancies occur during the study, those female subjects will be withdrawn from the study. Information will be collected as to the pregnancy course, outcome and health of the newborn infant. Because LA is available as an over the counter supplement, male subjects whose female partners become pregnant will continue in the study, however pregnancy and birth outcomes of the female partners will be recorded and presented to the DSMB.

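### Section 5.6b compares laboratory changes by arm without separating on-drug from off-drug samples, so the stop rules dilute late-visit mean differences towards no difference

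*Combined protocol and SAP*

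**What the plan says.** Section 5.6b gives the laboratory analysis in one sentence: "laboratory test results at baseline and changes from baseline will be summarized and compared using t-tests for continuous measures", with "Fisher's exact test for proportions". It does not say which visit is compared, what the proportions count, or whether a sample must fall within a period of exposure. The analysis set is equally open on exposure: "Only subjects that complete the baseline evaluation and take at least one dose of study drug will be included in the data analysis". Pill-count compliance is mentioned only for the mixed model of the walking outcome. For adverse events, the plan is to "compare the differences in the occurrence and the frequencies between the two groups".

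Section 5.1m ties dosing to the same laboratory values.

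- **Urine protein:** subjects with ACR above 300 mg/g "permanently stop study drug and receive referral to PCP or nephrologist".
- **eGFR:** a value below 50, or a value of 50-59.9 that is still below 60 on retest, leads to a permanent stop.
- **Liver:** Grade 2 or higher leads to a repeat test, then a 50% dose, then a stop. Return to full dose is possible if values improve.
- **Missed visits:** a subject who misses a visit pauses drug until the sample is drawn.

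On follow-up, the liver subsection of 5.1m says: "Subjects continue study procedures following the study flowsheet until study end during any investigational drug dose reductions and temporary cessations". Once the drug is judged no longer safe, section 5.7 says that subjects who "otherwise are able to participate in the study outcomes for the remainder of the study, they are encouraged to do so". Section 5.1d also expects some subjects to remain in the study after stopping drug for laboratory reasons, since it exempts them from unscheduled relapse visits.

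On the renal cases attributed to lipoic acid, section 2.0 reports: "To date, all three cases resolved within a 3-12 month period".

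**The concern.** Treatment is withdrawn because of the outcome being compared, and this will happen more often in the lipoic acid arm if the drug causes the abnormality. Once off drug, an affected subject either stays and may contribute recovered values, or leaves and contributes nothing. Both routes pull the late-visit mean change in the lipoic acid arm towards placebo.

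A near-zero laboratory difference late in the trial could then be read as reassurance about kidney and liver when it partly shows that the stop rules worked. Renal toxicity is an acknowledged risk of this drug in the protocol, so the comparison will be looked at closely.

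**Working it through.** The documents give no laboratory SD, event rate or expected difference, so there is no planned figure to reproduce for this comparison. The check has two parts: the text set side by side, and an illustration on assumed inputs.

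**Text**

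1. *Does any rule restrict samples to exposure?* No. Section 5.6b has none, the analysis set needs only a baseline and one dose, and pill counts belong to the walking model.
2. *Do the stop rules act on the compared variables?* Yes, for urine protein, eGFR and liver values. Dose halving for a laboratory value applies to liver only.
3. *Can off-drug samples enter?* Yes. Panels are scheduled at M3, M6, M12, M18 and M24 (5.5e), with urine protein also at M9, M15 and M21 (5.5a). Follow-up continues through reductions and temporary stops and is encouraged after permanent ones. A catch-up sample after a missed visit is taken during a pause, and no analysis rule identifies it.
4. *When does it matter?* M3 is the first scheduled panel after baseline, so an abnormality first found there arose on drug and dilution is minimal. It can build up at later visits.
5. *What else captures harm?* Section 6.3a always sends ALT/AST grade increases, new ACR above 300 and new eGFR below 60 to the database. Section 5.6b compares events by arm, and section 6.8 gives the DSMB these laboratory data by arm. Not on the always-report list are an eGFR fall of 25% or more that stays at or above 60 (a Medical Monitor notification in 5.1m), 1+ proteinuria with ACR at or below 300, and liver values other than ALT/AST.

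**Illustration**

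Sample size, from 5.6a: 44/(1 − 0.25) = 58.7, rounded up to 59 per arm. This reproduces the plan's figure.

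Assumed inputs, not from the documents:

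- f = share of lipoic acid subjects affected
- D = their on-drug shift in SD units
- r = fraction of that shift lost by the visit compared
- 1% placebo rate for threshold crossings

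Mean difference = f × D × (1 − r).

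SD² averaged over arms = [1 + 1 + f(1 − f)(D(1 − r))²]/2.

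Two-sided 0.05, normal approximation, 59 per arm.

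Example with f = 0.15 and D = 4:

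- r = 0: difference 0.15 × 4 = 0.60. SD² = (2 + 0.1275 × 16)/2 = 2.02, SD = 1.42. Power 0.63.
- r = 0.5: difference 0.30. SD² = (2 + 0.1275 × 4)/2 = 1.255, SD = 1.12. Power 0.31.
- r = 1: difference 0, rejection about 0.05.

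| f | D (SD) | Difference, r = 0 | Power | Difference, r = 0.5 | Power |
|---|---|---|---|---|---|
| 10% | 4 | 0.40 | 0.38 | 0.20 | 0.17 |
| 15% | 4 | 0.60 | 0.63 | 0.30 | 0.31 |
| 25% | 2 | 0.50 | 0.64 | 0.25 | 0.25 |
| 25% | 4 | 1.00 | 0.93 | 0.50 | 0.64 |

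With 44 per arm, the 15%, 4 SD row becomes 0.51 and 0.24.

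For the proportion ever crossing a threshold (Fisher's exact test, 59 per arm, against 1% on placebo), power is 0.04 at 5%, 0.39 at 10%, 0.76 at 15% and 0.99 at 25%. These values do not depend on r, because a crossing stays counted after recovery.

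The two tests answer different questions, so their power values should not be ranked against each other. What matters is that one moves with recovery and the other does not. The r = 0 column is also not the power of a worst-value analysis, which carries extra noise in both arms.

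**The case against.** The strongest reply is that the t-test is only one strand of the safety plan. The most important crossings are always reported whatever their intensity or attribution, adverse event frequencies are compared between arms, the DSMB sees the laboratory data by arm, and the same sentence of 5.6b includes Fisher's test for proportions. If those proportions mean subjects ever abnormal, recovery does not touch them. Comparing all treated subjects by arm is also a common safety summary, and no text says that M24 is the visit compared.

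Most of this stands. It rules out several stronger conclusions that a reader might draw.

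- **That the plan hides renal or liver harm.** It does not: listed crossings remain visible as events.
- **That stopped subjects are always kept in follow-up.** This is stated for reductions and temporary stops. After a permanent safety stop it is encouragement.
- **That every laboratory trigger leads to a halved dose.** Among laboratory triggers, only liver values do.
- **That the 3-12 month recovery gives the share of effect lost at M24.** It rests on three renal cases, with no liver figure. It would describe subjects still abnormal, not a mean change, and would pick the least favourable visit. Onset within the first year with recovery within 12 months gives nobody abnormal at M24 by construction.

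The reply does not remove the gap. Fisher's test is planned without saying what is counted or whether it is ever or at a visit. The changes outside the always-report list have no equivalent safeguard, so for them the by-arm laboratory comparison carries more of the weight.

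**Conclusion.** The point holds as dilution of the continuous comparison at later visits. The direction follows from the text, given only that abnormal values tend to improve after a reduction or stop, or that affected subjects leave.

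The size cannot be derived from the documents. It depends on how many subjects are affected, by how much, how fast each measure recovers and which visit is compared. In the illustration the mean difference falls in proportion to recovery: halved at half recovery and gone at full recovery. Changes in subjects who never meet a trigger and stay on drug are unaffected.

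The primary endpoint is not involved. The plan should be amended because the drug has acknowledged renal toxicity and a null late-visit difference would be hard to interpret.

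**What to change.** In section 5.6b, add the following by arm, with no change to any dosing or stopping rule.

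1. **Worst on-drug change from baseline per subject**, for continuous measures taken in everyone (for example eGFR, ALT, AST). Include the sample that triggered a reduction or stop and its retest, and state the window after last dose that counts as on drug.
2. **A definition of the Fisher proportions** as subjects ever meeting each 5.1m trigger while on drug. Use this rather than a t-test for ACR, which is measured only after 1+ proteinuria and so is not available in all subjects.
3. **Values after a reduction or stop**, shown separately as recovery data.
4. **The all-subject by-visit summary**, kept alongside. Restricting each late visit to on-drug subjects is no substitute, because affected subjects have left that group by then.

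Also require stop, pause and reduction dates for every subject, including those who stay in the study off drug. Section 5.7 states recording of the discontinuation date only for those who cannot continue procedures.

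The cost is some SAP wording, modest programming and, if the dates are not already captured, a small addition to data collection. One drawback is that a worst value depends on how many samples a subject gives, so on-drug time and number of samples should be shown by arm.

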3.0 Objectives

Hypothesis: The purpose of this study is to determine if the oral antioxidant LA provides clinical benefits and reduces brain atrophy in PMS. The hypothesis is that daily LA will both maintain mobility and reduce whole brain atrophy, thus paving the way for

consideration of LA as a disease-modifying therapy for PMS. The specific aims of this multi-center RCT of 1200mg oral daily LA versus placebo in PMS are:

Specific Aim 1. Determine if LA is superior to placebo in maintaining mobility as measured by the primary outcome of change in completion time of the Timed 25 Foot Walk (T25FW). Secondary outcomes are changes in the 2 Minute Timed Walk (2MTW) and fall count for consistency of the effects of LA on mobility.

Specific Aim 2. Determine if LA is superior to placebo in slowing whole brain atrophy with an estimated 40-50%% effect size. Additional secondary outcome measures are changes in neurological disability, cognition, mood, and quality of life.

Specific Aim 3. Monitor safety and tolerability via laboratory testing and adverse event reporting.

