5.0 Study Procedures

5.1 Study Design

5.1a. Design and specific aims: This is a phase 2, double-blind, multi-center RCT to compare the daily administration of 1200 mg oral LA to a placebo, as a disease-modifying treatment in PMS. A total of 118 subjects with PMS will be randomized 1:1 to LA or placebo. None of the study procedures involve usual care. All study procedures will be covered by study funding.

5.1b. Study population: A convenience sample of adults with PMS will be recruited from the study sites. The multi-site design of the trial is intended to promote generalizability of the study results.

5.1c. Study timeline and visit scheduling. The anticipated study recruitment period is for the first 18 months once the study is approved at the first study site or until enrolment is completed, whichever occurs first. The study will end when the last participant exits the study. There should be no more than 60 days inclusive between the screen and baseline visits. Subsequent study visits will occur at 3 months, 6 months, and every 6 months thereafter, each visit within +/- 2 weeks from the ideal visit based on the baseline/month zero (M0) visit. The MRI can take place up to 2 weeks prior to the baseline and final visits. Should the final MRI be postponed for any reason until after the

final visit, the subjects should continue taking study drug until the MRI has been done. Reasons for conducting visits outside the scheduling window are recorded.

Performance on clinical measures may be subject to variation due to the day-to-day fluctuations characteristic of PMS. Effects of fluctuations on study outcomes will be minimized by encouraging subjects to maintain their usual sleep, eating, and medication intake patterns on study days. Study visits will be scheduled at the same time-period each visit (morning versus afternoon). Study visits may be postponed for concurrent non-MS related illness affecting neurological performance on the discretion of the treating neurologist.

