5.1j. Randomization. The assignment of subjects to the treatment arms will be based on permuted block randomization defined by study site. The Central Research Pharmacy and SCC will oversee the randomization schedule. The Central Research Pharmacy will also maintain a master list of all study subjects in order to ship appropriate amounts of bulk study drug to the US site pharmacies for individual subject packaging and shipping.

5.1k. Compliance and medication reconciliation: Compliance with taking the investigational drug will be encouraged at each visit and between visits by telephone calls. Unused pills will be collected at each study visit and if necessary, by mail between visits. The study site research pharmacies will conduct medication reconciliation with returned pills and provide feedback to research staff to monitor if compliance is less than 75% or more than 125% of prescribed doses to encourage proper compliance.

5.11. Risks: Risks of the investigational drug, study procedures, and potential loss of confidentiality are reviewed with potential subjects during the informed consent process. Risks, reporting, responses to risks, and methods to minimize risks are further outlined in section 6.0, Reporting and 7.0, Privacy and Confidentiality. Briefly, risks of the

investigational drug are minimized by adverse event reporting safety and safety laboratory studies. Risks of study procedures are minimized by careful screening procedures and trained study personnel. Risks of loss of confidentiality are minimized by limiting collection of PHI, limiting access of PHI to the minimum necessary study staff, and use of secure data transfer methods.

Risks of LA: Oral LA can cause physical side effects including gastrointestinal (GI) intolerance, nausea and vomiting and rash. LA may cause liver, renal and urinary disorders. There is a possibility of developing proteinuria and/or membranous glomerulonephritis due to study drug. It is not known how LA could affect a fetus. LA may increase the risk of hypoglycemia in diabetics. The risks of LA taken with DMTs or with alcohol are unknown.

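### Section 5.6b plans significance tests but no effect estimates with intervals for safety, and a non-significant Fisher test would say little about an uncommon renal harm

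*Combined protocol and SAP*

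**What the plan says.** Section 3.0 makes safety the third specific aim: "Monitor safety and tolerability via laboratory testing and adverse event reporting". The last paragraph of section 5.6b is the whole safety analysis. Adverse and serious adverse events are tabulated and compared between groups, side effects by chi-square or Fisher. Laboratory values and changes from baseline are summarised and "compared using t-tests for continuous measures and Fisher's exact test for proportions". It names no effect measure, interval, upper bound or safety significance level.

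The protocol treats renal harm as a known possibility. On the pilot trial, section 2.0 now holds that the serious "adverse event of biopsy-proven glomerulonephritis and a second case of proteinuria in subjects in the LA cohort was related to lipoic acid". Section 5.1l tells subjects that "There is a possibility of developing proteinuria and/or membranous glomerulonephritis due to study drug".

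The sample size in section 5.6a comes from the Timed 25 Foot Walk and was checked against brain atrophy. No power or precision is given for safety.

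**The concern.** For an uncommon harm in a trial of this size, a test answers a question that the trial is too small to settle. The useful question for Aim 3 is how large an excess risk the data leave open. A p-value does not answer that, and a table of counts answers it only for a reader who works out the interval.

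At stake is the final report. If LA causes renal events at something like the pilot rate, the most likely inferential statement under the present plan is that the arms did not differ significantly. The t-test on mean laboratory change gives little protection. A harm confined to a few subjects is averaged over many unaffected ones, and under section 5.1m subjects with ACR above 300 mg/g permanently stop study drug, so their later values are off drug.

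**Working it through.** **Inputs from the documents**
- Section 5.1a: "A total of 118 subjects with PMS will be randomized 1:1 to LA or placebo", so 59 per arm.
- Section 5.6a: "A sample size of 44 per group will have 80% power", then "A sample size of 59 per arm will allow for a 25% drop-out rate". Check: 44 / (1 - 0.25) = 58.67, rounded up to 59. The plan's figure reproduces.
- Section 5.6a: "0.05 two-sided significance level", stated for efficacy.
- Section 2.0: two renal cases in the pilot LA arm; 51 pilot subjects in total.

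**Assumptions (not in the documents)**
- The same two-sided 0.05 applies to safety.
- The pilot LA arm had 24-27 subjects, so the rate is 2/27 = 7.4% to 2/24 = 8.3%. The exact 95% interval for 2/27 is 0.9% to 24.3%.
- The placebo rate is 0%, with 1% and 2% as sensitivity values.

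**Step 1. Cases needed for significance.** With k LA cases, no placebo cases and 59 per arm, the two-sided Fisher p-value is 2 x C(59,k) / C(118,k).

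| LA v placebo cases | p |
|---|---|
| 3 v 0 | 0.244 |
| 4 v 0 | 0.119 |
| 5 v 0 | 0.057 |
| 6 v 0 | 0.027 |

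At least 6 v 0 is needed.

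**Step 2. Power.** With no placebo cases, power = P(X ≥ 6), where X is binomial with n = 59 and the LA rate.

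| LA rate v 0% | Power | Missed |
|---|---|---|
| 5% | 7% | 93% |
| 2/27 = 7.4% | 27% | 73% |
| 2/24 = 8.3% | 37% | 63% |
| 10% | 55% | 45% |
| 15% | 89% | 11% |

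Placebo cases make it harder. Enumerating both binomials at 2/27, the miss rate is 83% with 1% on placebo and 89% with 2%.

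**Step 3. What an interval would show.** Take 4/59 v 0/59, a difference of 6.8%. The Wilson limits are 2.7% to 16.2% for LA and 0% to 6.1% for placebo. The Newcombe limits are:
- lower: 0.0678 - √[(0.0678 - 0.0267)² + 0.0611²] = -0.006
- upper: 0.0678 + √[(0.1618 - 0.0678)² + 0²] = 0.162

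So p = 0.12 goes with an interval of -0.6% to 16.2%. Even with no LA cases, the exact two-sided 95% upper limit for the LA rate is 1 - 0.025^(1/59) = 6.1%.

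**Step 4. The planned test applied to the pilot.** With 2 v 0 among 51 subjects (no placebo cases assumed), Fisher gives p between 0.22 and 0.49 for LA arms of 24-27. The harm now attributed to LA would have been non-significant.

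**The case against.** Much of the opposing case limits how far the point can be pressed.

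- **Denominator.** A reader might use 44 per arm, which pushes the miss rate at 2/27 v 0% to 90%. That is the efficacy number net of drop-out. Section 5.6b analyses everyone who completes baseline and takes a dose, section 5.7 encourages follow-up off drug and seeks an early termination visit, and the flowsheet has safety laboratory tests at M24. The relevant number is close to 59.
- **Rate.** Two cases give a very imprecise rate, seen under different monitoring from the present three-monthly urine testing. Over the interval 0.9% to 24.3% the miss rate at 59 per arm runs from about 100% to 0.2%. Hence the table rather than one figure.
- **Which test.** The figures are for Fisher. An uncorrected chi-square would miss about 36% at 2/27 v 0% with 59 per arm. But 6 cases in total mean 3 expected per arm, where Fisher is the usual choice, and Fisher is the test prescribed for laboratory proportions.
- **Other outputs.** A reader might infer that p-values are the only between-arm safety output. They are not. Counts are tabulated by group, section 6.3a requires new ACR above 300 mg/g and new eGFR below 60 to be reported whatever their attribution, and section 6.8 gives the DSMB quarterly reports by arm. These protect subjects during the trial; none supplies an estimate with its uncertainty for the final report.
- **Intent.** A reader might infer that the plan equates non-significance with safety. No passage says so. The pilot does not show it either: its renal cases were re-attributed by a later review of causality, not by re-reading a p-value.

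It is also fair that phase 2 trials are seldom powered for safety and that Aim 3 speaks of monitoring, not of excluding a margin. That favours estimation over testing.

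**Conclusion.** The point holds as a gap in the analysis method. Significance tests are the only inferential between-arm safety methods in section 5.6b, and no effect estimate with an interval accompanies them. For a renal harm near the pilot rate, Fisher at 59 per arm misses it about 63-73% of the time. That range rests on an assumed pilot LA arm of 24-27, no placebo cases and a two-sided 0.05 level. The size depends strongly on the true rate (93% missed at 5%, 11% at 15%), and section 2.0 mentions a third case without a denominator. The conclusion does not need the exact rate: with up to 5 v 0 cases the test is non-significant, while excess risks well above 10% remain compatible with the data. The documents do not support the stronger claims that all the planned tests share this miss rate or that the plan intends to read non-significance as safety. This is a worthwhile, cheap improvement, not a flaw in subject protection.

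**What to change.** Amend the safety paragraph of section 5.6b as follows.

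1. For subject-level events at any time on study, among all treated subjects, report number and percentage by arm and the LA-minus-placebo risk difference with a two-sided 95% interval (Newcombe or Miettinen-Nurminen, one chosen in advance). Use thresholds already in the protocol: new ACR above 300 mg/g (including the M9, M15 and M21 urine tests), new eGFR below 60, eGFR fall of 25% or more, liver values of Grade 2 or higher, and any SAE.
2. When no LA events occur, add the exact upper bound for the LA rate.
3. For continuous laboratory values, report the between-arm mean difference with a 95% interval.
4. Label safety p-values descriptive, and state that non-significance will not be taken as evidence of safety. Making the interval primary also settles disagreements such as 5/59 v 0/59, where the Newcombe interval is 0.7% to 18.4% but Fisher gives p = 0.057. No margin is needed, because the aim is to describe, not to decide.

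The cost is wording and a few table columns from data already collected; no subjects, visits or clinical rules change. The downside is that intervals will be wide and the safety statement less favourable.
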